#### 4.6 Duration of Therapy

Subjects should continue protocol therapy as described until:

- Disease progression (Note: treatment should continue until progression is confirmed by repeat scan approximately 6 weeks later to rule out pseudoprogression based on investigator discretion)
- Inter-current illness prevents further administration of treatment
- Unacceptable adverse event(s)

- Subject decides to withdraw from the study, OR
- General or specific changes in the subject's condition render the subjects unacceptable for further treatment in the judgment of the investigator.

#### 4.7 Duration of Follow Up

Subjects will be followed for up to 3 years after removal from study treatment for determination of OS. Subjects removed from study treatment for unacceptable AEs will be followed for resolution or stabilization of the adverse event(s). All subjects (including those withdrawn for AEs) should be followed after removal from study treatment as stipulated in the protocol.

#### 4.8 Removal of Subjects from Protocol Therapy

Subjects will be removed from protocol therapy and the PI notified when any of the criteria listed in section 4.6 apply. The reason for discontinuation of protocol therapy will be documented on the eCRF.

In case a subject decides to prematurely discontinue protocol therapy (“refuses treatment”), the subject should be asked if she or he may still be contacted for further scheduled study assessments. The outcome of that discussion should be documented in both the medical records and in the eCRF.

Excessive subject withdrawals from protocol therapy or from the study can render the study un-interpretable; therefore, unnecessary withdrawal of subjects should be avoided.

#### 4.9 Study Withdrawal

If a subject decides to withdraw from the study (and not just from protocol therapy) an effort should be made to complete and report study assessments as thoroughly as possible. At the time of withdrawal, the investigator should attempt to establish as completely as possible the reason for the study withdrawal.

- The subject should be asked if they are willing to allow for the abstraction of relevant information from their medical record in order to meet the long term follow up (e.g., survival) objectives outlined in the protocol.
- A complete final evaluation at the time of the subject's study withdrawal should be obtained with an explanation of why the subject is withdrawing from the study.
- If the subject is noncompliant and does not return for an end of study follow up assessment, this should be documented in the eCRF.
- If the reason for removal of a subject from the study is an adverse event, the principal specific event will be recorded on the eCRF.

October 01,,  
2020

Excessive subject withdrawals from protocol therapy or from the study can render the study un-interpretable; therefore, unnecessary withdrawal of subjects should be avoided.

## 5.0 DRUG INFORMATION

### 5.1 Panitumumab (Vectibix®)

For additional information, refer to the Panitumumab Investigator's Brochure (IB) and the prescribing information for Vectibix® (panitumumab) available at the link provided: [http://pi.amgen.com/united\\_states/vectibix/vectibix\\_pi.pdf](http://pi.amgen.com/united_states/vectibix/vectibix_pi.pdf)

#### 5.1.1 Description, Packaging and Labeling

Panitumumab is supplied as a sterile, colorless, preservative-free solution containing 20 mg/mL panitumumab in a single-use vial. Panitumumab is a sterile, colorless, pH 5.6 to 6.0 liquid for intravenous (IV) infusion, which may contain a small amount of visible translucent-to-white, amorphous, proteinaceous, panitumumab particulates.

Panitumumab is provided in 12 units/kit and 6 units/kit. Each single-use 10 mL vial contains 200 mg of panitumumab, 58 mg sodium chloride, 68 mg sodium acetate, and Water for Injection, USP. Each single-use 20 mL vial contains 400 mg of panitumumab, 117 mg sodium chloride, 136 mg sodium acetate, and Water for Injection, USP. Panitumumab kit description is as follows:

- (200mg) Panitumumab, 20 mg/ml, 10 ml vial, 12 units/kit
- (400mg) Panitumumab, 20mg/ml, 20ml vial, 6 units/kit

#### 5.1.2 Storage and Handling

Store vials in the original carton under refrigeration at 2° to 8°C (36° to 46°F) until time of use. Protect from direct sunlight. DO NOT FREEZE. Since panitumumab does not contain preservatives, any unused portion remaining in the vial must be discarded.

#### 5.1.3 Dose, Schedule and Administration

See section 4.3

#### 5.1.4 Preparation

See the panitumumab prescribing information for preparation instructions.

#### 5.1.5 Stability

The diluted infusion of panitumumab should be used within 6 hours of preparation if stored at room temperature, or within 24 hours of dilution if stored at 2° to 8°C (36° to 46°F). DO NOT FREEZE.

### 5.1.6 Return and Retention of Panitumumab

Unused vials will be handled per instructions from Amgen, Inc. Partially used and completely used vials will be destroyed per institutional guidelines.

### 5.1.7 Adverse Events Associated with Panitumumab

The most common adverse events ( $\geq 20\%$ ) with panitumumab monotherapy are skin rash with variable presentations, paronychia, fatigue, nausea, and diarrhea. The adverse events listed below have been reported in subjects receiving panitumumab. See section 4.4.1 for further instruction on the management adverse events associated with panitumumab therapy.

- Dermatologic and soft tissue toxicity
- Increased tumor progression, increased mortality, or lack of benefit in *RAS*- and *KRAS*-mutant mCRC
- Electrolyte depletion
- Infusion reactions
- Acute renal failure in combination with chemotherapy
- Pulmonary fibrosis/interstitial lung disease
- Photosensitivity
- Ocular toxicities
- Increased mortality and toxicity with panitumumab in combination with bevacizumab and chemotherapy

## 5.2 Nivolumab (Opdivo®)

See the Nivolumab Investigator's Brochure (IB) and the prescribing information for Opdivo® (Nivolumab) at [http://packageinserts.bms.com/pi/pi\\_opdivo.pdf](http://packageinserts.bms.com/pi/pi_opdivo.pdf) for more detailed information.

### 5.2.1 Description

Nivolumab (BMS 936558-01\*) injection drug product is a sterile, non-pyrogenic, single-use, isotonic aqueous solution formulated at 100mg/10 mL. The vials supplied contain 100 mg. Nivolumab is a sterile, preservative-free, non-pyrogenic clear to opalescent, colorless to pale-yellow liquid that may contain light (few) particles for IV administration. Nivolumab will be supplied by Bristol-Myers Squibb (BMS) at no charge to study subjects.

\*Nivolumab may be labeled as BMS936558-01 solution for injection.

### 5.2.2 Packaging and Labeling

Primary Packaging (Volume)/Label type: Carton of 5  
Secondary Packaging (Qty)/Label type: 10-cc Type 1 flint glass vials stoppered with butyl stoppers and sealed with aluminum seals.

### 5.2.3 Storage and Handling

Store nivolumab under refrigeration at 2°C to 8°C (36°F-46°F) in the original package until time of use. Protect from light and freezing. Do not shake the vial.

If stored in a glass front refrigerator, vials should be stored in the carton. Recommended safety measures for preparation and handling of nivolumab include laboratory coats and gloves.

For additional details on prepared drug storage and use time of nivolumab under room temperature/light and refrigeration, please refer to the BMS-936558 (nivolumab) Investigator Brochure section for “Recommended Storage and Use Conditions”.

The investigator should ensure that the study drug is stored in accordance with the environmental conditions (temperature, light, and humidity) as per product information and the Investigator Brochure and per local regulations. It is the responsibility of the investigator to ensure that investigational product is only dispensed to study subjects. The investigational product must be dispensed only from official study sites by authorized personnel according to local regulations. If concerns regarding the quality or appearance of the study drug arise, the study drug should not be dispensed and contact BMS immediately.

#### **5.2.4 Dose, Schedule and Administration**

See section 4.3

Nivolumab will be given every two weeks at a dose of 240 mg, to be administered as a 30-minute IV infusion.

Subjects may be dosed no less than 12 days from the previous dose of drug. There are no premedications recommended for nivolumab on the first cycle.

The dosing calculations should be based on the actual body weight at baseline. If the subject’s weight on the day of dosing differs by > 10% from the weight used to calculate the original dose, the dose must be recalculated. All doses should be rounded to the nearest milligram. There will be no dose modifications allowed.

Subjects should be carefully monitored for infusion reactions during nivolumab administration. If an acute infusion reaction is noted, subjects should be managed according to institutional guidelines (See section 4.5.2).

Doses of nivolumab may be interrupted, delayed, or discontinued depending on how well the subject tolerates the treatment.

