## 4.0 TREATMENT PLAN

### 4.1 Schema

#### 4.1.1 Rationale for Doses Selected

We plan to perform a single-arm, open-label, multicenter Phase II clinical trial of nivolumab 240 mg IV q2wk, ipilimumab (1 mg/kg IV q6wk), and panitumumab (6 mg/kg IV q2wk), after a safety lead-in cohort of a total of 6 subjects has completed 12 weeks of combination therapy at the proposed starting doses. The starting doses and schedule were carefully selected after consideration of existing clinical studies and preclinical data. The efficacy of ipilimumab monotherapy is dose-dependent, but the rate and severity of immune-related adverse events is also dose-dependent. The FDA-approved dose of combination ipilimumab and nivolumab in management of metastatic melanoma is ipilimumab 3 mg/kg IV q3wk for four doses combined with nivolumab 1 mg/kg IV q3wk; followed by nivolumab monotherapy 240 mg flat dose IV q2wk. Notably, studies of combination ipilimumab and nivolumab have started both antibodies concurrently, with the rationale that preclinical models showed that the combination is synergistic only when administered concurrently rather than sequentially, and so we plan to administer the investigational drugs concurrently as well. Subsequent clinical trials have investigated combinations of ipilimumab and nivolumab that would attenuate the frequency and severity of immune-related adverse events without mitigating efficacy. The efficacy and toxicity profiles of more infrequent dosing of ipilimumab combined with nivolumab were studied in a phase I study in subjects with chemotherapy-naïve recurrent stage IIIB or IV NSCLC, CheckMate 012. In this study, treatment with ipilimumab 1 mg/kg q6wk combined with nivolumab 3 mg/kg q2wk was much better tolerated than treatment with ipilimumab 1 mg/kg q3wk combined with nivolumab 3 mg/kg q3wk. Additional dosing combination regimens tested revealed inferior efficacy when nivolumab dosing was decreased to 1 mg/kg. Treatment with ipilimumab 1 mg/kg q6wk combined with nivolumab 3 mg/kg q2wk resulted in a 33% rate of grade 3-4 treatment-related AEs, but only 13% rate of treatment-related AEs leading to study drug discontinuation (compared to 19% grade 3-4 treatment-related AEs and 10% treatment-related AEs leading to discontinuation in nivolumab 3 mg/kg IV q2wk arm). The FDA has determined that based on population pharmacokinetics models, there is a negligible difference in overall exposure between nivolumab 240 mg IV q2wk and 3 mg/kg IV q2wk. Consequently, we plan the ipilimumab and nivolumab dosing within safety cohort 1 to be ipilimumab 1 mg/kg IV q6wk plus nivolumab 240 mg IV q2wk. The dose of panitumumab selected within dose level 1 is the FDA-approved monotherapy dose.

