### 4.3 Treatment Dosage and Administration

Dosing should be based on the subject's baseline weight on day 1 of cycle 1, as measured according to institutional standards; doses will be adjusted for subjects who experience a  $\geq 10\%$  change in weight during the study.

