#### 4.3.1 Safety Cohort 1 Schedule (3-drug combination)

REGIMEN DESCRIPTION – Safety Cohort 1 )					
Agent	Premedications; Precautions	Dose/Frequency	Route	Schedule	Cycle Length
Panitumumab	See Section 4.5 and 4.5.1	6mg/kg every 2 weeks	IV (specific details below)	D1, D15, D29 of each cycle	
		For doses $\leq 1000$ mg	IV over 60 ( $\pm 15$ ) minutes		
		For doses $>1000$ mg,	IV over 90 ( $\pm 15$ ) minutes		
Ipilimumab	See Section 4.5.3	1 mg/kg every 6 weeks	IV over 30 ( $\pm 15$ ) minutes	D1 of each cycle	
Nivolumab	See sections 4.5.2 and 4.5.3	240 mg every 2 weeks	IV over 30 ( $\pm 15$ ) minutes	D1, D15, D29 of each cycle	

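### Section 5.2.4 orders the fixed 240 mg nivolumab dose to be recalculated after a weight change but gives no mg/kg factor, so the instruction cannot be carried out as written and must be reconciled with section 4.3.

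*Combined protocol and SAP*

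**What the plan says.** Protocol section 4.1.1 sets out the regimen as "nivolumab 240 mg IV q2wk, ipilimumab (1 mg/kg IV q6wk), and panitumumab (6 mg/kg IV q2wk"). Nivolumab is a fixed amount; the other two drugs are dosed per kilogram. The regimen tables in 4.3.1 and 4.3.2 both list nivolumab as "240 mg every 2 weeks".

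Section 5.2.4, on nivolumab alone, refers the reader to 4.3 and repeats the amount: "Nivolumab will be given every two weeks at a dose of 240 mg, to be administered as a 30-minute IV infusion". The same section then adds four rules:

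- Dosing calculations start from the weight measured at baseline.
- Recalculation is mandatory after a large enough change: "weight on the day of dosing differs by > 10% from the weight used to calculate the original dose, the dose must be recalculated".
- Doses are rounded to whole milligrams.
- Changes are barred in one short sentence: "There will be no dose modifications allowed".

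It goes on to permit interruption, delay or discontinuation according to tolerance.

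The introduction to section 4.3 bases dosing on day 1 weight in cycle 1 and says that "doses will be adjusted for subjects who experience a" change in weight of at least 10%. It does not limit this to the drugs dosed per kilogram.

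**The concern.** A fixed 240 mg dose is not computed from a weight. It therefore has no original weight to compare against, no factor to reapply and nothing to round. Yet the recalculation in 5.2.4 is mandatory, and it stands in the section that pharmacy and site staff would consult for this drug.

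The trigger would be noticed, because section 6.3 has weight recorded at every treatment visit. Section 9.5 requires the trial to be run exactly as the protocol describes, emergencies aside. A site that keeps 240 mg after a weight change of more than 10% departs from 5.2.4, and a site that changes the dose departs from the regimen table.

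The trial is multicenter, and nivolumab belongs to both the three-drug and the two-drug regimen, so the ambiguity could reach any subject, including those in the safety lead-in. If sites resolved it differently, nivolumab dose would vary with site and with weight change, and the response and toxicity rates would describe a less uniform regimen than the tables show.

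**Working it through.** The plan states no figure for a recalculated nivolumab dose, so there is nothing to reproduce. The check is a comparison of the texts, followed by a short illustration.

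**1. Is there a factor from which to recalculate?**

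| Drug | Amount in 4.1.1 and the regimen tables | Per-kg factor | Weight rule in its own drug section |
|---|---|---|---|
| Panitumumab | 6 mg/kg every 2 weeks | yes | none; 5.1.3 refers to 4.3 |
| Ipilimumab | 1 mg/kg every 6 weeks | yes | none in 5.3.4 |
| Nivolumab | 240 mg every 2 weeks | no | recalculation and rounding in 5.2.4 |

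The only drug section with a recalculation rule belongs to the only drug without a per-kg factor.

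**2. Does section 4.3 settle it?** No. Its weight rule speaks of doses in general, neither including nor exempting nivolumab. Its trigger is a change of at least 10%; that of 5.2.4 is more than 10%. The two differ only at exactly 10%.

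**3. Can a site comply with everything after, say, an 11% weight loss?** Keeping 240 mg satisfies the table but not the recalculation order. Changing the dose satisfies the order but not the table. No section says which prevails.

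**4. How far apart could the readings be?** Both rules below are assumptions; the protocol orders neither.

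- Assumption A: 240 mg is scaled in proportion to weight.
  - 11% loss: 240 × 0.89 = 213.6, rounded to 214 mg
  - 11% gain: 240 × 1.11 = 266.4, rounded to 266 mg
  - 20% loss: 240 × 0.80 = 192 mg
  - 20% gain: 240 × 1.20 = 288 mg
- Assumption B: a site borrows the 3 mg/kg that 4.1.1 mentions for comparison. This equals 240 mg only at 240 / 3 = 80 kg. After an 11% loss:
  - baseline 60 kg: 3 × 60 × 0.89 = 160.2, rounded to 160 mg
  - baseline 80 kg: 3 × 80 × 0.89 = 213.6, rounded to 214 mg
  - baseline 100 kg: 3 × 100 × 0.89 = 267 mg

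For a 100 kg subject who loses 11%, the three readings give 240 mg (table), 214 mg (A) and 267 mg (B). They disagree even on the direction of the change, which is what it means for the recalculation to have no defined result. Much of the spread under B comes from moving to a per-kg dose at all, not from the weight change, so B should not be read as the effect of losing weight.

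**The case against.** The strongest reply is that 240 mg is clearly the protocol dose. It appears in 4.1.1, in both regimen tables and in 5.2.4 itself ("Nivolumab will be given every two weeks at a dose of 240 mg"). The tables give per-kg factors for the other two drugs and none for nivolumab, so the rule in 4.3 reads most naturally as applying to those two. With no factor to apply, many sites would simply give 240 mg. Section 4.1.1 also reports, from population pharmacokinetic models, that "there is a negligible difference in overall exposure between nivolumab 240 mg IV q2wk and 3 mg/kg IV q2wk". This tempers any expected effect on response or toxicity. All of this stands as a limit on the likely consequence. It does not make the mandatory sentence in 5.2.4 executable.

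Two stronger readings are tempting, and the documents do not support them.

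- A reader might infer that 5.2.4 forbids any change of dose, so that the section contradicts itself a second time. But the same section goes on to allow interruption, delay and discontinuation. The action column in the tables of 4.4.2 and 4.4.2.1 is headed as dose modification, yet the actions it gives for nivolumab are to withhold or stop, with no reductions. The ban plausibly means no toxicity-driven reductions, and in that sense it is compatible with a fixed dose. The text does not say so, which calls for clarification, not for deleting the sentence.
- A reader might infer that doses will in fact differ by site, or that the efficacy result is compromised. The documents show only that differing doses are possible.

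**Conclusion.** The inconsistency holds, within limits. Section 5.2.4 pairs a fixed 240 mg dose with a mandatory weight-based recalculation that lacks a factor, and section 4.3 adds a weight rule of unstated scope with a slightly different trigger. Nothing elsewhere in the protocol resolves this.

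The size in milligrams cannot be derived from the documents. The 192 to 288 mg range for weight changes of minus to plus 20% rests on proportional scaling, which the protocol never orders, and serves as illustration only. The point does not touch the sample size, the error rates or the primary analysis. It is a drafting conflict in a dosing instruction, and this review takes no position on which rule is right.

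**What to change.** In the next amendment, the sponsor should reconcile the introduction to 4.3, the tables in 4.3.1 and 4.3.2, and section 5.2.4:

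- State in one place whether body weight affects the nivolumab dose, and make the calculation, recalculation and rounding sentences in 5.2.4 consistent with that decision.
- Name in 4.3 the drugs to which the weight rule applies.
- Use one trigger throughout, either at least 10% or more than 10%.
- Say whether the ban on dose modifications in 5.2.4 refers to toxicity-driven changes.

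The cost is a few words in two sections. No visit, assessment or analysis needs to be added.

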#### **5.2.5 Preparation**

See the nivolumab prescribing information for preparation instructions. Nivolumab Injection, 100 mg/10 mL (10 mg/mL) is to be administered as an IV infusion through a 0.2-micron to 1.2-micron pore size, low-protein binding polyether sulfone membrane in-line filter at the protocol-specified dose. It is not to be administered as an IV push or bolus injection. Nivolumab injection can be

infused undiluted (10 mg/mL) or diluted with 0.9% Sodium Chloride Injection, USP or 5% Dextrose Injection, USP to protein concentrations as low as 1 mg/mL. Care must be taken to assure sterility of the prepared solution as the product does not contain any antimicrobial preservative or bacteriostatic agent.

### 5.2.6 Stability

After preparation of infusion, from a microbiological point of view, the product should be used immediately. If not used immediately, chemical and physical in-use stability of nivolumab has been demonstrated for 24 hours at 2°C to 8°C protected from light and a maximum of 8 hours at 20°C-25°C and room light (this 8-hour period of the total 24 hours should be inclusive of the product administration period).

### 5.2.7 Return and Retention of Nivolumab

Unused vials will be handled per instructions from BMS. Partially used and completely used vials will be destroyed per institutional guidelines.

### 5.2.8 Adverse Events Associated with Nivolumab

The adverse events listed below have been reported in subjects receiving NVB. See section 4.4 for further instruction on the management of adverse events associated with nivolumab therapy.

- Immune-mediated pneumonitis: Defined as requiring use of corticosteroids and no clear alternate etiology, including fatal cases have occurred with nivolumab treatment.
- Immune-mediated colitis: Defined as requiring use of corticosteroids and no clear alternate etiology, including fatal cases have occurred with nivolumab treatment.
- Immune-mediated hepatitis: Defined as requiring use of corticosteroids and no clear alternate etiology have occurred with nivolumab treatment.
- Immune-mediated endocrinopathies: Hypophysitis, adrenal insufficiency, hypo- and hyper-thyroidism, and type I diabetes mellitus have occurred with nivolumab treatment.
- Immune-mediated nephritis and renal dysfunction: Defined as renal dysfunction or  $\geq$ Grade 2 increased creatinine, requirement for corticosteroids, and no clear alternate etiology, can occur with nivolumab treatment.
- Immune-mediated rash: Severe rash (including rare cases of fatal toxic epidermal necrolysis) can occur with nivolumab treatment.
- Immune-mediated encephalitis: Withhold nivolumab in subjects with new-onset moderate to severe neurologic signs or symptoms.
- Other immune-mediated adverse reactions: Monitor for as described in section 4.4.2
- Infusion reactions: Severe infusion reactions have been reported in <1.0% of subjects in clinical trials of nivolumab. See section 4.5.2 for information on the management of nivolumab-related infusion reactions.
- Other events may occur. One event that has been observed is hemolytic anemia

### 5.3 Ipilimumab (Yervoy®)

See the Ipilimumab Investigator's Brochure (IB) and the prescribing information for Yervoy® (Ipilimumab) at [http://packageinserts.bms.com/pi/pi\\_yervoy.pdf](http://packageinserts.bms.com/pi/pi_yervoy.pdf) for more detailed information.

